6.3.1.3 Cyclosporine dose modification due to increase in blood pressure

Cyclosporine can cause blood pressure increase. After informed consent is obtained follow [Table 7-1](#) and [Section 7.2.2.2](#) for regular blood pressure monitoring guidelines.

If there is an increase in blood pressure, treatment with an appropriate antihypertensive agent must be initiated. Preference must be given to an antihypertensive agent that does not interfere with the pharmacokinetics of cyclosporine.

Potassium-sparing drugs must not be used as hyperkalemia can occur. If there is no improvement in blood pressure, cyclosporine dose must be decreased by 25% to 50%. Cyclosporine must be discontinued if antihypertensive treatment(s) and dose decreases do not result in return to baseline blood pressure.

6.3.1.4 Cyclosporine dose modification due to nephrotoxicity

After informed consent is obtained follow [Table 7-1](#) and [Section 7.2.2.5](#) for regular serum creatinine and BUN monitoring. Cyclosporine can cause nephrotoxicity.

The cyclosporine induced nephrotoxicity is usually associated with elevation of serum creatinine and blood urea nitrogen (BUN) levels. These changes are usually dependent on the cyclosporine dose and initially reversible with a dose reduction. In general, fine-tuning of the cyclosporine dose to the lower end of the therapeutic range, adequate hydration, optimization of blood pressure control, and avoidance of other nephrotoxic agents, can improve the safety and tolerability.

A peripheral blood smear evaluation is recommended to rule out hemolytic uremic syndrome.

If the serum creatinine is greater than or equal to 25% above the patient's pre-treatment level, serum creatinine must be repeated within two weeks. In the interim, increase of fluid intake and decrease dose of other concomitant nephrotoxic medications (e.g., antibiotics) is recommended.

If the change in serum creatinine remains greater than or equal to 25% above baseline, Cyclosporine may be reduced by 25% to 50%. If at any time the serum creatinine increases by greater than or equal to 50% above pretreatment level, the cyclosporine must be reduced by 25% to 50%. Cyclosporine must be discontinued if reversibility (within 25% of baseline) of serum creatinine is not achievable after two dose modifications.

6.3.2 Dose adjustments for QTcF prolongation

In case of QTcF >500 msec, (or QTcF prolongation >60 msec from baseline)

1. Assess the quality of the ECG recording and the QT value and repeat if needed
2. Interrupt study treatment
3. Determine the serum electrolyte levels (in particular hypokalemia, hypomagnesemia). If abnormal, correct abnormalities before resuming study drug treatment.
4. Review concomitant medication associated with QT prolongation, including drugs with a "Known", "Possible", or "Conditional risk of Torsades de Pointes" (refer to www.qtdrugs.org), and drugs with the potential to increase the risk of study drug exposure related QT prolongation
5. Check study drug dosing schedule and treatment compliance

6. Consider collecting a time-matched PK sample, and record time and date of last study drug intake.

After confirming ECG reading at site, if QTcF > 500 msec

- Interrupt study treatment
- Repeat ECG and confirm ECG diagnosis by a cardiologist or central ECG lab
- If QTcF confirmed > 500 msec:
 - Correct electrolytes, eliminate culprit concomitant treatments, and identify and address clinical conditions that could potentially prolong the QT as per the ECG and QTc Clinical Safety Standards Guidelines Section 3.3.1.
 - Consult with a cardiologist (or qualified specialist)
 - Increase cardiac monitoring as indicated, until the QTcF returns to \leq 480 msec.
- After resolution to \leq 480 msec, consider re-introducing treatment at reduced dose, and increase ECG monitoring for the next treatment(s):
 - If QTcF remains \leq 500 msec after dose reduction, continue planned ECG monitoring during subsequent treatment
 - If QTcF recurs > 500 msec after dose reduction, discontinue patient from study.

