1.2.1.3 Clinical Pharmacokinetics

1.2.1.3.1 Pharmacokinetics of eltrombopag in adults

Eltrombopag human PK in plasma has been described in healthy volunteers and in patients within the targeted disease indications including patients with ITP, hepatitis C virus (HCV), and solid tumors. Eltrombopag PK in patients with ITP or solid tumors is generally similar to

that observed in healthy subjects. Data in SAA patients is limited to preliminary results in 23 SAA patients (3 of them being ██████) from study NIH 12-H-0150 (ELT116643/CETB115AUS01T) normalized to a dose of 150 mg daily. Exposure (AUC_{tau}, C_{max}) in these patients was 2 to 3 times higher than exposure observed in healthy volunteers or ITP patients, and consistent with exposure observed in HCV patients.

In general, exposure to eltrombopag increased with increasing doses with no major deviation from dose-proportionality. Eltrombopag is absorbed with a peak concentration occurring 2 to 6 hours after oral administration. Based on urinary excretion and biotransformation products eliminated in feces, the oral absorption of drug-related material following administration of a single 75-mg solution of [¹⁴C]-eltrombopag was estimated to be at least 52%.

A standard high-fat breakfast decreased plasma eltrombopag AUC_{inf} by approximately 59% and C_{max} by 65% and delayed T_{max} by 1 hour. The calcium content of this meal may have also contributed to this decrease in exposure by chelation. Co-administration of 75 mg of eltrombopag with a polyvalent cation-containing antacid (1.524 mg aluminum hydroxide, 1.425 mg magnesium carbonate, and sodium alginate) to 26 healthy adult subjects decreased plasma eltrombopag AUC_{inf} and C_{max} by approximately 70%. It is therefore recommended to take eltrombopag at least 2 hours before or 4 hours after other medications (e.g., antacids), calcium-rich foods (e.g., dairy products and calcium-fortified juices), or supplements containing polyvalent cations such as iron, calcium, aluminum, magnesium, selenium, and zinc.

The predominant route of eltrombopag excretion is via feces (59%), and 31% of the dose is found in the urine. Unchanged eltrombopag in feces accounts for approximately 20% of the dose. Only metabolites are detected in urine.

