7.2.2.8 Cardiac assessments

7.2.2.8.1 Electrocardiogram (ECG)

A standard 12 lead ECG will be performed as per the assessment plan in [Table 7-1](#), [Table 7-2](#) and [Table 7-6](#).

Table 7-6 Local ECG collection plan

Visit	Day	Time	ECG Type
Screening	1	Pre-dose	12 Lead, triplicate
D1	1	Pre-dose	12 Lead, triplicate
Week 26 (6M) or EOT eltrombopag	1	Pre-dose	12 Lead, triplicate
Week 53 (1Y)*	1	Pre-dose	12 Lead, triplicate
Month 24 (2Y) or EOT cyclosporine*	1	Pre-dose	12 Lead, triplicate
Unscheduled sample		Anytime	12 Lead, triplicate

*only for responders.

Interpretation of the tracing must be made by a qualified physician and documented on the ECG eCRF page. Each ECG tracing should be labeled with the study number, patient initials (where

regulations permit), patient number, date, and kept in the source documents at the study site. Clinically significant findings must be discussed with Novartis prior to enrolling the patient in the study.

TriPLICATE ECG must be performed, the individual ECGs must be recorded approximately 2 minutes apart. The mean QTcF value for each visit must be calculated from the triplicate ECGs for each patient.

Additional, unscheduled, safety ECGs may be repeated at the discretion of the investigator at any time during the study as clinically indicated. Unscheduled ECGs with clinically significant findings should be collected in triplicate. Local cardiologist ECG assessment may also be performed at any time during the study at the discretion of the investigator.

Clinically significant ECG abnormalities present at screening should be reported on the Medical History eCRF page. New or worsened clinically significant findings occurring after informed consent must be recorded on the Adverse Events eCRF page.

7.2.2.8.2 Cardiac imaging - MRA (magnetic resonance angiography), MUGA (multiple gated acquisition) scan or echocardiogram

Not applicable.

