2.1.2 General analysis conventions

Data from all study centers will be pooled for analyses.

Qualitative data (e.g., gender, race, etc.) will be summarised by absolute and relative frequencies. A missing category will be included where applicable. Percentages will be calculated using the number of patients in the relevant analysis set or subgroup as the denominator.

Quantitative data (e.g., age, body weight, etc.) will be summarised by appropriate descriptive statistics (i.e. mean, standard deviation (sd), minimum, 25th percentile, median, 75th percentile and maximum).

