2.7.4 Other safety data

2.7.4.1 ECG

12-lead ECGs, including QTcF (Fridericia's correction), mean heart rate (HR), PR-, QT- and QRS-durations, will be obtained locally for each patient during the study. ECG data will be read and interpreted locally.

Where ECG replicates are provided for an assessment, the average of the ECG parameters at that assessment will be used in the analyses.

The number (%) of patients with notable values will be presented.

Table 2-3 Notable criteria for ECG parameters

Parameter	Notable low value	Notable high value
QTcF		New value of >450 and \leq 480 ms New value of >480 and \leq 500 ms New value of >500 ms Increase from baseline of >30 ms to \leq 60 ms Increase from baseline of >60 ms
Heart rate	Decrease >25% from baseline and to a value <50 bpm	Increase >25% from baseline and to a value >100 bpm
PR	--	Increase >25% from baseline and to a value >200 ms New value of >200 ms
QRS	--	Increase >25% from baseline and to a value >120 ms New value of >120 ms

A listing of all ECG assessments will be produced. Notable values as well as values measured outside of on-treatment period will be flagged in the listings.

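### No ECG is scheduled during the eltrombopag course before its closing visit, so the QTcF rule has no planned reading to act on in that period, and the SAP's ECG table should count only patients with an ECG and separate the two treatment periods

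*Protocol*

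**What the plan says.** **The rule.** Protocol section 6.3.2 opens with its trigger: "In case of QTcF >500 msec, (or QTcF prolongation >60 msec from baseline". Study treatment is then interrupted, electrolytes and co-medication are reviewed, and a branch for confirmed values above 500 msec follows. In that branch, once QTcF has come down to 480 msec or less, the investigator may "consider re-introducing treatment at reduced dose, and increase ECG monitoring for the next treatment(s". If QTcF stays at or below 500 msec on the reduced dose, the instruction is to "continue planned ECG monitoring during subsequent treatment". If it exceeds 500 msec again, the patient is discontinued.

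**The schedule.** Section 7.2.2.8.1 refers to Tables 7-1, 7-2 and 7-6. Table 7-6 lists screening, Day 1, "Week 26 (6M) or EOT eltrombopag", Week 53, and Month 24 or end of cyclosporine. All are triplicate and pre-dose, and the last two are for responders only. A further row allows unscheduled ECGs at any time. The ECG row of Table 7-1 agrees: screening, baseline and Week 26.

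**The analysis.** SAP section 2.7.4.1 states: "The number (%) of patients with notable values will be presented". Its QTcF categories are new values above 450, 480 and 500 ms and rises of more than 30 and 60 ms. SAP section 2.1.2 sets the general denominator: "Percentages will be calculated using the number of patients in the relevant analysis set or subgroup as the denominator". SAP section 2.1.3 defines the on-treatment period as running to 30 days after the last dose of either drug.

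**The concern.** A monitoring rule works only if there are readings for it to act on. Section 6.3.2 reads as though planned ECGs accompany treatment with the combination, but the schedule puts the first of them at the visit where eltrombopag stops. A site that re-introduces eltrombopag mid-course, completes the phase of increased monitoring and then returns to planned monitoring finds nothing planned until eltrombopag ends.

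The same gap limits the safety table. For the period on both drugs, the only scheduled on-treatment evidence is one pre-dose reading per patient, at or near the end. If that reading is pooled with ECGs taken a year or more later on cyclosporine alone, and divided by everyone treated whether or not they had an ECG, a low percentage could be read as evidence about QTcF on the combination that was never collected.

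**Working it through.** The plan gives no figure to reproduce here. The check is a count from the schedule and a look at the denominator.

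**1. Visits and ECGs in the eltrombopag course** (protocol section 7.1, Tables 7-1 and 7-6)
- Scheduled visits: Weeks 1 to 8 weekly = 8; Weeks 10, 12, ..., 26 = 9; total 17.
- Visits with an ECG: Week 1 (Day 1, pre-dose) and Week 26 (pre-dose) = 2.
- Visits without an ECG: 17 − 2 = 15, all consecutive (Weeks 2 to 8 = 7; Weeks 10 to 24 = 8).
- Gap: (26 − 1) × 7 = 175 days, in effect the whole course, since section 6.1.1.1 ends eltrombopag at 6 months regardless of response.

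**2. Scheduled post-baseline ECGs per patient**
- Non-responders and patients who leave by Week 26: 1.
- Responders who continue: up to 3. Week 53 falls (53 − 26) × 7 = 189 days after Week 26, and Month 24 about 24 × 30.4375 − 52 × 7 = 366.5 days after that.
- Only the first of the three belongs to the eltrombopag period.

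**3. What one end-of-course reading can detect** (illustration)
- Assumption: a QTcF episode lasting d weeks has its onset spread evenly over the 25 weeks.
- The chance that it is present at the Week 26 ECG is d/25. For d = 1, 2, 4 and 8 this is 4%, 8%, 16% and 32%.

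**4. Timing within the day**
- Protocol section 1.2.1.3.1: "Eltrombopag is absorbed with a peak concentration occurring 2 to 6 hours after oral administration". A pre-dose reading misses that window.

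**5. Effect of the denominator**
- Let N be the safety set, m the number without a post-baseline ECG in the period, and k the number with a notable value. By the general convention the table shows k/N. Among patients who could show a notable value the proportion is k/(N − m). The relative understatement is m/N.
- Enrollment closed at 54 (SAP section 1). I take N = 54, assuming all were dosed. The documents do not give m, so a range is shown:

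| m (assumed) | k = 1: k/N | k = 1: k/(N − m) | m/N | k = 0: one-sided 95% upper bound, 1 − 0.05^(1/(N − m)) |
|---|---|---|---|---|
| 0 | 1.9% | 1.9% | 0% | 5.4% |
| 5 | 1.9% | 2.0% | 9.3% | 5.9% |
| 10 | 1.9% | 2.3% | 18.5% | 6.6% |

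- With k = 0 the percentage is zero either way, and only the bound moves.
- For the cyclosporine-only period the whole-set denominator fails by design, because only responders have those ECGs. If there were just 17 responders, the SAP's success threshold for 54 patients, at most 17/54 = 31% of the set could contribute a scheduled reading.

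**The case against.** **The rule is not without inputs.** Section 6.3.2 asks for increased ECG monitoring on re-introduction before planned monitoring resumes, and re-introduction is itself discretionary. Unscheduled ECGs are allowed at any time, and section 6.4.3 calls for close ECG monitoring with certain QT-relevant co-medication. Entry criteria screen out high QTcF, cardiac disease and risk factors for Torsades de Pointes. Chemistry, including potassium and magnesium, is checked at every visit for six months. All of this stands and lowers the stakes, but none of it puts a planned ECG inside the course.

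**Pre-dose is not drug-free.** With the half-life of 26 to 35 hours that the protocol gives for ITP patients, simple decay leaves 0.5^(24/26) = 53% to 0.5^(24/35) = 62% after 24 hours. This is fair. The readings should be labelled, not dismissed.

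**The SAP may already cope.** Section 2.1.2 also provides for a missing category where applicable, and the table shells are a separate document. Section 2.7.4.1, however, names neither a missing category nor a denominator, so the text leaves the general convention in force.

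**Three stronger readings fail.**
- A reader might infer that no scheduled ECG can ever trigger the rule. Study treatment includes cyclosporine, which responders still take at Weeks 26 and 53, so those ECGs can trigger its interruption.
- A reader might see a contradiction between the 60 msec limb and the 480 msec value. That value sits in the branch for readings above 500 msec. The 60 msec limb has no QTcF value for resuming, which is a gap, not a conflict.
- A reader might set discontinuation from the study against the follow-up required by section 6.3.3. The protocol elsewhere pairs study discontinuation with follow-up, so the two are compatible.

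**Conclusion.** The point holds for the eltrombopag course. For 15 consecutive visits, within a gap of 175 days, no ECG is scheduled, and the planned monitoring named in section 6.3.2 corresponds to no ECG before the one that closes the course. These passages need to be reconciled. The count rests only on the protocol's own tables.

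The reporting consequence also holds, but its size is unknown. Dilution equals m/N, and the documents do not state m. It would be tempting to take the on-treatment deaths described in the Amendment 2 rationale as m and quote a percentage, but nothing says whether those patients had a post-baseline ECG.

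Nor does the QTcF table rest on one reading for everybody. Responders contribute up to three scheduled ECGs, and unscheduled on-treatment ECGs are not excluded. What is limited to one scheduled reading per patient is the evidence for the eltrombopag period, and that reading is pre-dose. The primary endpoint is unaffected.

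**What to change.** **Protocol.** Reconcile section 6.3.2 with Tables 7-1 and 7-6 so that the text and the schedule agree on what planned ECG monitoring means while eltrombopag is being given. How to do so is a clinical choice for the sponsor. Enrollment ended on 11-May-2020 and the primary-analysis lock was on 09-Dec-2020, after all patients had completed or left the first six months. This is now a clarification for the record and for the final study report, and it cannot change monitoring already carried out.

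**SAP section 2.7.4.1**, in time for the final report:
- Replace the analysis-set denominator for notable values with patients who have a baseline ECG (where the criterion needs one) and at least one post-baseline ECG in the period summarised. Show the number without one.
- Report the eltrombopag period (Week 26 or end of eltrombopag, plus unscheduled ECGs in that period) separately from the cyclosporine-only period (Week 53 and Month 24). Unscheduled ECGs can be assigned by the last date of each drug, which SAP section 2.1.3 already defines.
- State how many scheduled and unscheduled ECGs contribute, since responders have up to three scheduled chances to show a notable value and others have one.
- Label scheduled readings as pre-dose.

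**Cost.** Wording and table programming only, with no new data. The downside is a less reassuring QTcF statement, because the eltrombopag-period evidence will be shown to be thin.

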6.3.3 Follow-up for toxicities

Patients whose treatment is interrupted or permanently discontinued due to an adverse event or clinically significant laboratory value, must be followed-up at least once a week (or more frequently if required by institutional practices, or if clinically indicated) for 4 weeks, and subsequently at approximately 4-week intervals, until resolution or stabilization of the event, whichever comes first. Appropriate clinical experts should be consulted as deemed necessary.

All patients must be followed-up for adverse events and serious adverse events for 30 days following the last dose date of study treatment (eltrombopag and/or cyclosporine).

6.3.3.1 Dose delays, modifications or discontinuation for hematologic side effects

Patients who experience a deep venous thrombosis (other than a line-related upper extremity thrombosis) or a pulmonary embolus, a transient ischemic attack or stroke, or a myocardial infarction at any time while on eltrombopag must discontinue eltrombopag but may remain on cyclosporine.

6.3.3.2 Dose delays, modifications or discontinuation for non-hematologic side effects

Infection

Patients who experience an infection requiring intravenous antibiotics must not discontinue eltrombopag or cyclosporine. If the patient experiences infection severe enough to require vasopressors or intubation, eltrombopag and cyclosporine must be interrupted until the patient is clinically stable.

6.3.4 Anticipated risks and safety concerns of the study drug

Thrombotic/Thromboembolic complications

The risk of thromboembolic events (TEEs) has been found to be increased in patients with chronic liver disease treated with 75 mg eltrombopag once daily for two weeks in preparation for invasive procedures. Six of 143 (4%) adult patients with chronic liver disease receiving eltrombopag experienced TEEs (all of the portal venous system) and two of 145 (1%) patients in the placebo group experienced TEEs (one in the portal venous system and one myocardial infarction). Five of the 6 patients treated with eltrombopag experienced the thrombotic complication at a platelet count $>20,000/\mu\text{L}$ and within 30 days of the last dose of eltrombopag. Eltrombopag is not indicated for the treatment of thrombocytopenia in patients with chronic liver disease in preparation for invasive procedures.

In eltrombopag clinical studies in ITP, TEEs were observed at low and normal platelet counts. Caution should be used when administering eltrombopag to patients with known risk factors for thromboembolism including but not limited to inherited (e.g., Factor V Leiden) or acquired risk factors (e.g., ATIII deficiency, antiphospholipid syndrome), patients with prolonged periods of immobilization, malignancies, contraceptives and hormone replacement therapy, surgery/trauma, obesity and smoking. Platelet counts should be closely monitored and dose modifications must be made in accordance with parameters provided in the protocol. The risks of thromboembolism and any of the following complications versus the benefit of improved platelet counts must be evaluated by the Investigator for each patient with known risks of TEEs.

Risk of hepatotoxicity

Eltrombopag administration can cause hepatobiliary laboratory abnormalities, severe hepatotoxicity and potentially fatal liver injury. In the controlled clinical studies in chronic ITP with eltrombopag, increases in serum ALT, AST and bilirubin were observed. Hepatotoxicity should be monitored and eltrombopag must be discontinued if hepatobiliary abnormalities are observed as described in [Section 6.3.3.2](#).

Exercise caution when administering eltrombopag to patients with hepatic disease.

Ophthalmic changes

Cataracts were observed in toxicology studies of eltrombopag in rodents ([Section 1.2.1.1.3](#)), but has not been reported at significant rates over control groups in human studies. In controlled studies in thrombocytopenic patients with HCV receiving interferon therapy (n = 1439), progression of pre-existing baseline cataract(s) or incident cataracts was reported in 8% of the eltrombopag group and 5% of the placebo group. Retinal hemorrhages, mostly Grade 1 or 2, have been reported in HCV patients receiving interferon, ribavirin and eltrombopag (2% of the eltrombopag group and 2% of the placebo group). Hemorrhages occurred on the surface of the retina (preretinal), under the retina (subretinal), or within the retinal tissue. Ophthalmologic monitoring defined per protocol should be performed and eltrombopag continuation reconsidered in case of suspected cataract development or worsening or in case of retinal hemorrhages. In clinical studies of eltrombopag in SAA cataracts have not been reported.

Bone marrow reticulin formation and risk of bone marrow fibrosis

Eltrombopag may increase the risk for development or progression of reticulin fibers within the bone marrow. The relevance of this finding, as with other TPO-R agonists, has not been established yet.

If immature or dysplastic cells not linked to primary disease are observed, peripheral blood smears should be examined for new or worsening morphological abnormalities (e.g., teardrop and nucleated red blood cells, immature white blood cells) or cytopenia(s). If the patient develops new or worsening morphological abnormalities or cytopenia(s) not linked to primary disease, treatment with eltrombopag must be discontinued and a bone marrow biopsy considered, including staining for fibrosis.

Progression to existing myelodysplastic syndrome

TPO-R agonists are growth factors that lead to thrombopoietic progenitor cell expansion, differentiation and platelet production. The TPO-R is predominantly expressed on the surface of cells of the myeloid lineage. For this class of TPO-R agonists, there is a concern that they may stimulate the progression of existing hematopoietic malignancies such as myelodysplastic syndrome.

In clinical studies with a TPO-R agonist, romiplostim and eltrombopag, in patients with MDS, cases of transient increases in blast cell counts were observed and cases of MDS disease progression to AML were reported.

In the CETB115AUS01T study, eltrombopag in combination with IST was assessed in patients with SAA. Published results indicate that clonal cytogenetic evolution with dysplastic changes occurred at a similar frequency compared to NIH historic experience with standard IST (10-15%) ([Townsley 2017](#)). All patients should be monitored regularly for new or worsening morphological abnormalities or cytopenia(s), and may require bone marrow evaluation, as clinically indicated.

Eltrombopag must be discontinued in case of suspected myeloproliferation not linked to the primary disease or if there is a suspected myeloproliferation due to eltrombopag treatment.

Bleeding events after study drug discontinuation

Following discontinuation of eltrombopag, platelet counts return to baseline levels within 2 weeks in the majority of patients, which increases the bleeding risk and in some cases may lead to bleeding. Platelet counts should be monitored as per protocol following discontinuation of eltrombopag.

